## 11.0 Specimen Collection and Banking (if applicable)

N/A. No specimens will be collected or banked.

## **13.0 Provisions to Monitor the Data to Ensure the Safety of Subjects (if applicable)**

**Overall framework for monitoring:** Participant safety will be monitored by the research therapist and PI who are licensed, registered occupational therapists as well as the study co-I who is an experienced stroke rehabilitation nurse. The risks of this study include subject fatigue, Pain, embarrassment, and loss of privacy.

**Frequency of monitoring:** Therapy sessions will be conducted by a licensed occupational therapist. Heart rate and blood pressure will be recorded before, during and after each session and the study therapist will closely monitor the subject for possible pain or fatigue by having subjects complete a self-reported summary of pain and fatigue using a Borg rating scale. In previous work we demonstrated that the functional tasks practiced in a session were at a difficulty level that matched or slightly exceeded the subjects' movement ability level, therefore we do not expect that the patient will show movement compensations. To further assure that movement compensations do not emerge and cause pain or injury, aspects of each task such as object weight, speed of performance or surface heights will be manipulated by the therapist.

**Process for reporting adverse events:** The PI, Co-I, research therapist and/or project coordinator will be responsible for reporting adverse events as per the policies and procedures of the MUSC Institutional Review Board.

**Trial monitoring:** the PI and co-I will be responsible for trial monitoring and assure that the trial is conducted according to the approved protocol. Because this trial is low risk, i.e., no greater risk than a traditional outpatient occupational therapy rehabilitation program, the PI and co-PI are appropriate monitors. The study team will meet at a minimum each week to identify and address any safety issues but can meet immediately if an urgent issue arises. In addition, the building in which this study will take place has offices for several of the MUSC COBRE in Stroke Recovery investigators who are experienced stroke MDs. As needed, an MD can immediately be consulted.

## **14.0 Withdrawal of Subjects (if applicable)**

**Subject Voluntary Withdrawal:** As participation in this study is voluntary, the subject has the right to withdraw from the study at any time for any reason without prejudice to his/her future stroke rehabilitation care. For the subject who withdraws consent, the date and reason for withdrawal will be documented. Subject data will be included in the analyses up to the date of withdrawal and no further data will be collected.

**Subject removal from the study:** The PI may stop study therapy if there is a safety concern (e.g., excessive pain/fatigue, hospitalization), if the subject fails to attend evaluation sessions or adhere to study procedures. Subject data will be included in the analyses up to the date of withdrawal and no further data will be collected.

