### **SA1: Determine the feasibility of implementing the TEAAC program:**

The primary endpoint will be a determination of the feasibility of the e-learning + therapy program. Primary outcome will be feasibility defined as (1) subjects' level of engagement in the program, (2) acceptability, (3) technological literacy, and (4) practicality. Data will be analyzed qualitatively.

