### 3.0 Intervention to be studied (if applicable)

The **3-month** intervention studied is called **Training to Empower Activity-dependent-plasticity-based Arm-use-habits in the Community and at Home (TEAAC)**. TEAAC has two components: An Online Educational Course and an In-Clinic Rehabilitation Therapy Program.

The TEAAC design and testing timepoints are indicated in the **figure to the left**. Subjects will be tested (see below) at enrollment (Baseline, evaluation timepoint 1, E1)), at the midpoint of the therapy + online program (1.5 months, E2), immediately following the in-clinic therapy + online program (3 months, E3), and 2 months after the program for follow up (5 months, E4).

**TEAAC e-learning:** 3-months of online educational modules include neuroscience education (based on an effective pain educational model) to improve patient self-efficacy, and strategy-training to improve patients' problem-solving abilities for at-home arm use. The course is live on the MUSC MoodleCE platform.

**TEAAC in-clinic therapy:** 24 in-clinic sessions; 3 times/week for 4 weeks (month 1), 2 times/week for 4 weeks (month 2) and 1 time/week for 4 weeks (month 3) with 200 movement repetitions per session. In our RCTs, this therapy dose required ~1.0-1.5 hours/session. A critical element of TEAAC is the focus on linking in-clinic therapy to out-of-clinic real world paretic arm use via MoodleCE Learning Activities.

	month 1	month 2	month 3	month 4	month 5	month 6	month 7	month 8	month 9	month 10	month 11	month 12
N=12	TEAAC Group 1 (n=4)		TEAAC Group 2 (n=4)			TEAAC Group 3 (n=4)		Group1 f/u tests		Group2 f/u tests		Group3 f/u tests

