## 4.0 Study Endpoints (if applicable)

**Primary Endpoint:** The primary endpoint will be determined in Specific Aim 1, the baseline to post intervention feasibility of the e-learning + therapy program. Outcome measures will include baseline to post intervention changes in participant scores on assessments of health literacy and technological literacy as well as their overall qualitative experiences.

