**Audio and Video Recording:**

- Audio Recording: Each subject will participate in 3 focus groups; one at baseline, immediately following the end of the 5-month intervention, and at the post-intervention follow up. The purpose of the focus groups will be to understand the participants' experiences with regards to the feasibility of the program and changes in his/her self-management skills. Each focus group will be audio recorded. The audio recording will be transcribed. The transcription will be analyzed using qualitative data analyses techniques to ascertain thematic data.
- Video Recording: Subjects will be video recorded during administration of two arm movement tests: the Fugl Meyer Assessment of the Upper Extremity and Wolf Motor Function Test. Trained assessment raters who are blind to testing time point will score the assessments from the video tapes. All videos will be stored on secured, password protected servers behind the MUSC firewall. The procedure for training raters and scoring from videos was developed in the PIs research laboratory and has been used in past and ongoing stroke rehabilitation research clinical trials. Of note- the only people having access to the videos are laboratory personnel who have been approved by the IRB to be part of this study, and who have completed all required IRB privacy and university training.

**Primary and Secondary outcome measures** are identified in the schedule of events table below.

Measurement Construct	Assessment method	Baseline (E1)	Mid (E2)	Post (E3)	Follow up (E4)
SA1: Primary Endpoint: Feasibility					
Health Literacy	Short Assessment of Health Literacy	X		X	
Tech Literacy	Technology Literacy self-evaluation	X		X	
Participants' experiences	Qualitative (focus group)	X		X	
SA2: Secondary Outcomes: Initial efficacy in the following areas:					
SA2a. Effect on self-confidence and social-support					
Self-Efficacy	PROMIS Self-Efficacy for Managing Daily Activities assessment	X		X	X
Social Isolation	PROMIS Social Isolation assessment	X		X	X
Emotional Support	PROMIS Emotional support assessment	X		X	X
SA2b. Effect on self-management skills					
Self-Management Skills	Qualitative (focus group)	X		X	X
SA2c. Effect on arm movement abilities					
Arm movement Impairment	Fugl-Meyer Assessment of the Upper Extremity (FMA-UE)	X	X	X	X
Arm motor function	Wolf Motor Function Test (WMFT)	X	X	X	X
Paretic arm use in the home	Wrist Worn Accelerometry	X	X	X	X

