- Possible risk: Loss of privacy due to the focus groups. A focus group is a discussion group and therefore it is possible that a stroke survivor may reveal information about him/herself during the discussion. This information may cause embarrassment. It is also possible that a focus group member inadvertently shares information outside the focus group. The focus group leader will remind members of this possible risk, that participation is voluntary, and to respect each other's privacy.

**Source Records:** All data about subjects will be collected from the subjects themselves. No other medical records will be accessed in this study.

**Data Collection Procedures:** Subjects will be assessed by trained evaluators who will be members of the study team. The following constructs will be measured by the following methods:

- Short Assessment of Health Literacy is an 18-item test designed to assess an adult's ability to read and understand common medical terms. It will be administered by the

study therapist in a standardized manner. Subjects' receive 1 point for each correct item. A score below 14/18 indicates poor health literacy.

- Technology Literacy self-evaluation is a 23-item questionnaire in which the subject answers true/false to questions about his/her readiness to participate in an online course. Any items in which the subject answers "false" will be reviewed with the subject by the study team in efforts to remedy the lack of technological confidence or literacy.
- Participants' Experiences and Participants' Self-Management Skills: Participants' viewpoints on the course will be assessed qualitatively using focus groups. A focus group guide will structure these sessions. The focus groups will be led by the co-I, [name] who is an experience focus group leader and has the necessary expertise for qualitative data analyses.
- Self-Efficacy will be assessed using the NIH PROMIS Self-Efficacy for Managing Daily Activities assessment. This is an 8-item assessment where a participant reports his/her level of confidence in doing 8 daily activities such as performing household chores, lift/carry groceries and shop/run errands.
- Social Isolation will be assessed using the NIH PROMIS Social Isolation assessment. This is an 8-item patient self-report assessment indicating patients' frequency (never, rarely, sometimes, usually, always) having feelings such as being left out, detached, isolated etc.

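### When the PI stops therapy before the 3-month evaluation (E3), assessment stops too, so the post-programme literacy, PROMIS and focus-group data come only from subjects not removed or withdrawn before E3

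*Combined protocol and SAP*

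**What the plan says.** Section 14.0 has two paragraphs. The first covers voluntary withdrawal and adds that "For the subject who withdraws consent, the date and reason for withdrawal will be documented". The second, on removal from the study, begins "The PI may stop study therapy if there is a safety concern" (excessive pain or fatigue and hospitalization are its examples). It adds two further grounds, missed evaluation sessions and a failure to "adhere to study procedures. Subject data will be included in the analyses up to the date of withdrawal and no further data will be collected". The closing data sentence is the same in both paragraphs.

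Section 1.0 (SA1) defines feasibility as subjects' "level of engagement in the program, (2) acceptability, (3) technological literacy, and (4) practicality". Section 4.0 lists, among the primary endpoint measures, "baseline to post intervention changes in participant scores on assessments of health literacy and technological literacy", together with qualitative experience. Section 1.0 (SA2) plans change scores from baseline to 3 months, and a 5-month assessment of retention.

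Section 10.0 uses the focus groups to learn about participants' "experiences with regards to the feasibility of the program and changes in his/her self-management skills", and its Data Collection Procedures confirm that participants' "viewpoints on the course will be assessed qualitatively using focus groups". Section 12.0 plans description and plots and states no missing-data method.

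**The concern.** Stopping a treatment and leaving a study are different events. A subject whose therapy has been stopped can still complete a questionnaire or join a focus group. Section 14.0 does not separate the two, and no other section provides E3 or E4 assessment for a subject who is off therapy but still consents.

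The loss is selective. Pain, fatigue, hospitalization and non-adherence are what a study of acceptability and practicality needs to hear about. Under the present rule the post-programme focus group, the literacy changes and the PROMIS changes lean towards people who tolerated and followed the programme. Section 12.0 says the project should help plan for pitfalls in a later implementation trial, and removed subjects are among those best placed to describe them.

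**Working it through.** **Inputs.** The rule comes from Section 14.0, the schedule from the table in Section 10.0, the visit times from Section 3.0 (E2 at 1.5, E3 at 3 and E4 at 5 months), and N = 12 from Section 6.0. The plan gives no figure for removals, so there is none to reproduce. The engagement calculation behind N = 12 does not enter.

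**Step 1: count the assessments.** The focus group appears in two rows of the schedule (experiences and self-management) and is counted once.

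| Assessment | Number | E1 | E2 | E3 | E4 |
|---|---|---|---|---|---|
| Health literacy | 1 | X | | X | |
| Technology literacy | 1 | X | | X | |
| Focus group | 1 | X | | X | X |
| PROMIS scales | 3 | X | | X | X |
| FMA-UE, WMFT, accelerometry, SIS-H | 4 | X | X | X | X |

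Total: 1 + 1 + 1 + 3 + 4 = 10. Taken at E2: 4. Not taken at E2: 10 − 4 = 6. Taken at E4: 1 + 3 + 4 = 8. All three SA1 rows are among those not taken at E2.

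**Step 2: apply the Section 14.0 rule by time of removal.**

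- Before E2: no scheduled post-baseline evaluation on any of the 10. Weekly FMA-UE keyform scores up to the stop remain (Section 3.0).
- Between E2 and E3: 4 assessments have an E2 value; the other 6 have no post-baseline value.
- Between E3 and E4: all 10 have an E3 value; only the 8 E4 assessments are lost.

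The audio-recording text in Section 10.0 places the second focus group after a 5-month intervention, whereas Section 3.0 gives 3 months. I used the schedule table (E3). On neither timing is there a focus group at E2.

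**Step 3: size.** With k subjects removed before E3, the share of the sample without E3 data is k/12: 1/12 = 8%, 2/12 = 17%, 3/12 = 25%.

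**Step 4: how often (illustration only).** Let q be an assumed chance of removal or withdrawal before E3, independent across subjects. The expected number assessed at E3 is 12(1 − q). The chance of losing at least one subject is 1 − (1 − q)^12.

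| Assumed q | Expected number at E3 | Chance of at least one lost |
|---|---|---|
| 3% | 11.6 | 0.31 |
| 5% | 11.4 | 0.46 |
| 10% | 10.8 | 0.72 |
| 25% | 9.0 | 0.97 |

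The nearest figure in the plan is the anticipated non-engagement of 5% or fewer (Section 12.0). That is not a removal rate, and using it as one is my assumption. At 5%, the expected loss is 12 × 0.05 = 0.6 subjects.

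**The case against.** The strongest reply is that this is a small, uncontrolled, descriptive pilot with no hypothesis test. Removal is at the PI's discretion. Sections 10.0 and 15.0 describe rest, rescheduling and adjusted intensity as responses to pain or fatigue, so removal is not the only course. The paragraph is headed as removal from the study, so the rule may be deliberate. All of this stands as a limit on how much data will be lost. It does not change what happens to a subject who is removed, and the loss is the same whether or not the rule was intended.

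Second, a subject stopped for missing evaluations might give no E3 data under any rule. This also stands. The loss that is clearly due to the sentence concerns subjects stopped for safety, and non-adherers who would still have come.

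Two stronger readings are tempting. A reader might infer that the engagement measure is distorted too. The documents do not support that: data up to removal are kept, and completion of the programme's activities is most naturally counted against the full schedule. A reader might also infer that less-engaged subjects who are not removed will all be seen at E3, so that removal is the only source of selection. Nothing in the plan says so, and Section 14.0 itself expects some missed evaluations.

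**Conclusion.** The concern holds as a matter of the plan's own wording. Stopping therapy ends assessment even for a subject who still consents. If that happens before E3, 6 of 10 distinct assessments have no post-baseline value. The literacy changes, the PROMIS changes and the post-programme focus group then describe only subjects not removed or withdrawn before E3. Removal between E3 and E4 costs E4 data only.

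The size is 8% of the sample per case. Confidence is high on the text and low on the practical effect, because the documents give no removal rate. A reader might infer from N = 12 that the feasibility results will be seriously biased. That would need a removal rate the plan does not provide, and the range in the working is only an illustration. The point merits a short amendment because the correction is cheap and the lost information bears on the study's main question. No view is taken on when therapy should be stopped.

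**What to change.** 1. Leave the PI's discretion to stop therapy unchanged.
2. In Section 14.0, limit the sentence that ends data collection to subjects who withdraw consent.
3. Invite subjects whose therapy was stopped, and who still consent, to E3 and E4 at 3 and 5 months from their own baseline. Fixing calendar times is necessary because Section 3.0 places E3 immediately after the programme, which has no clear meaning for someone stopped early. Offer at least the assessments scheduled at each visit among the literacy tests, PROMIS scales and focus group. Where therapy was stopped for a safety concern, leave the physical tests to the PI's judgement.
4. Report the number assessed at each timepoint and the reason for stopping. Section 14.0 now asks for a documented reason only when consent is withdrawn.

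The cost is a short amendment and up to two already scheduled visits per stopped subject. Subjects may decline, and those who were already missing evaluations may not come, so the loss is reduced rather than removed.

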## **15.0 Risks to Subjects**

The risks to the subjects are related to the therapy intervention are no greater than an outpatient stroke rehabilitation program. These risks include fatigue and pain.

- **Fatigue:** Although most of the upper extremity rehabilitation activities will occur while the subject is seated, it is possible that subjects become fatigued as a result of participating the therapy intervention. In our past studies (including an RCT with n=103 stroke survivors) using the same or similar therapy protocol, subjects routinely reported fatigue during and immediately following the therapy session. However, the level of fatigue was rated as an average of 3-5/10 on a self-report Likert scale. This was considered low to moderate fatigue, and in no case limited subjects' ability to carry on with their day. If subjects in the present study report fatigue during therapy,
- **Pain:** In our past stroke rehabilitation RCT (n=103) ~60% of subjects reported some level of pain in the paretic arm. In 10% of those cases (n=11), the pain was severe enough that the therapist recommended that the see a primary care physician. In most of cases, the therapist adjusted the intensity of therapy to reduce pain level (e.g., reduced the height of the tasks practiced, provided assistance).
- **Loss of confidentiality due to e-learning course participation:** it is possible that participating in the online course will cause subjects to lose confidentiality because others in the course will know their name. To mitigate this risk, we will offer subjects opportunity to choose their own username when logging into the course. This will enable them to remain anonymous.
- **Embarrassment:** It is also possible that subjects will be embarrassed by the e-learning course because lessons or assignments may showcase a weak area (e.g., something the subject has difficulty doing). Subjects will be informed that they can “opt out” of any assignment or discussion as they wish. Also, subjects will be shown how to delete a post in the e-learning course forum and discussion boards in case they have second thoughts about something they wrote.
- **Loss of privacy due to focus group discussions.** It is possible that a focus group member may share information about another focus group member outside of the group. The study team will remind focus group members that participation is voluntary and to respect each other's privacy.
- **Loss of confidentiality due to breach of data:** [name] team will take appropriate steps to protect subject data. However, there is a slight risk that information could be revealed inappropriately or accidentally. All hard-copy information with the subject's name on it will be stored in a locked cabinet in a locked office in a secure building at the MUSC ([name]). All electronic information will be stored in a secured database on the firewall protected MUSC network. No PHI will be transmitted outside of MUSC, stored on portable electronic devices, shared or sold at any time. All the data from the test results will be de-identified before it is stored in a research database

## 16.0 Potential Benefits to Subjects or Others

We expect that subjects will improve their own skills for managing their stroke. For example, we anticipate that subjects will know more about stroke, stroke recovery, and develop skills that promote increased use of the paretic arm in the home and community environments. However, it is possible that subjects do not have any direct benefit.

Although the subjects may not benefit individually, we will understand more about the feasibility of providing online education to this patient population.

## 17.0 Sharing of Results with Subjects

The study will be registered as a clinical trial at clinicaltrials.gov. All data will be shared as per clinicaltrials.gov requirements. In addition, each subject can request a copy of his/her own data at any time during the study.

## 18.0 Drugs or Devices (if applicable)

N/A. There are no drugs or devices studied.

